### 7.2. Analysis of Efficacy Data

#### 7.2.1. Analysis of Primary Efficacy Endpoint

For each cohort, the ORR per RECIST 1.1 will be summarized using FAS, along with 95% exact confidence interval using Clopper-Pearson method.

To determine the consistency of treatment effect across various demographics and baseline subgroups, the ORR (with a nominal 95% confidence interval [CI]) may be estimated within each category of the following subgroup variables: age, gender, race, ECOG, prior therapy.

#### 7.2.2. Analyses of Secondary Efficacy Endpoints

For each cohort:

- DCR will be summarized, along with 95% exact confidence interval using Clopper Pearson method.
- TTR will be summarized descriptively and using Kaplan-Meier method.
- DOR will be summarized descriptively and using Kaplan-Meier method.
- PFS and OS will be summarized using Kaplan-Meier method. Kaplan-Meier curves will be presented.
- Response in injected and noninjected target lesions by Investigator assessment
- Waterfall plots, spider plots, and swimmer plots will also be presented.

All secondary efficacy endpoints may be analyzed per cohort per subgroups specified for the primary endpoint as appropriate.

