1.2.1. Rationale for Intratumoral Administration of TLR9 Agonists

Administration of vidutolimod IT is intended to activate tumor-associated pDCs, and subsequently induce and activate anti-tumor CD8 $^{+}$ T cells within the tumor and tumor-draining lymph nodes where tumor-specific antigen is most likely to exist. Systemic administration of TLR9 agonists is

expected to result in uptake by the liver, spleen, and reticuloendothelial system, which may lead to suboptimal activation of pDCs in tumor and tumor-draining lymph nodes.

IT administration of vidutolimod is expected to activate resting tumor-associated pDCs thereby overcoming their tumor-promoting phenotype and ultimately inducing an antitumor CD8⁺ T cell response in the tumor microenvironment and/or in the tumor-draining lymph nodes. In preclinical models, IT dosing of TLR9 agonists was more effective than distant subcutaneous (SC) dosing, and induced regression not only in the directly injected tumor lesion, but also distant metastases (Shirota, 2012)(Lemke-Miltner, 2020).

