2.1.3. Exploratory Objectives

The exploratory objectives of this study are to:

- Evaluate the effect of vidutolimod in combination with cemiplimab on injected and noninjected target lesions
- To demonstrate treatment induced immune effects consistent with vidutolimod mechanism of action, including TLR9 signaling, increase in pDC activation, corresponding increase in CD8 T cell tumor infiltration, and activation status

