3.2.1. Treatment Beyond Progression

Subjects with a single tumor assessment of PD (per RECIST v1.1) may continue treatment until the next tumor assessment, at the discretion of the investigator based on the clinical state of the patient after communication with the Sponsor, if the following conditions are met:

- The subject has no decline in performance status (as defined by ECOG)
- The subject has absence of clinical symptoms or signs indicating clinically significant disease progression; absence of rapid disease progression or threat to vital organs or critical anatomical sites (eg, central nervous system metastasis, respiratory failure due to tumor compression, spinal cord compression) requiring urgent alternative medical intervention
- The subject has no significant, unacceptable or irreversible toxicities related to study treatments, including any AE(s) that would require permanent discontinuation of either vidutolimod or cemiplimab
- The subject provides consent prior to resuming treatment; this will be done by repeating the informed consent process that was conducted prior to initial study enrollment, with the subject signing (or having their legally authorized representative sign, as appropriate) the current version of the informed consent form (ICF)

Subjects will continue on the same schedule of assessments, with treatment continuing according to the next scheduled clinic visit (ie, treatments missed outside of the visit window will not be made up). As a general rule, if further progression occurs after study treatment is resumed ($\geq 20\%$ increase in tumor measurements by RECIST 1.1 criteria, using the initial progression scan as the comparator, and/or development of new lesions) that study drugs will be discontinued.

Treatment beyond the second progression may be allowed in selected cases after communication with the Sponsor (e.g., progression of lesion(s) that has(have) not been injected at the time of documented progression if the plan to inject the progressing lesion(s) after documented progression).

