4.1.1.3.1. Tumor Selection

Cutaneous, SC, and/or nodal tumors that are visible, palpable, or detectable by ultrasound or CT guidance are acceptable for IT injection. Systematic support from interventional radiology is required in case of IT injections to visceral lesions. For subjects who have lesions that are not externally visible, guidance on tumor selection and IT injections is included in a separate procedure manual.

Vigilance should be used when selecting lesions for injection that are in close proximity to critical structures (e.g. major airways).

- Special attention and judgment should be exercised before injection of a lesion in the following areas: the “mask areas” of the face (central face, eyelids, eyebrows, periorbital nose, lips [cutaneous and vermillion], chin, mandible, preauricular and postauricular skin/sulci, temple, ear, genitalia, hands, and feet).
- Unsuitable sites for intratumoral or subcutaneous injection would include, for example, the palm of the hand or the sole of the foot.
- Tumors should be at least 0.5 cm in longest diameter and need not be the largest lesion. A visceral tumor may be injected with the use of interventional radiology if, in the opinion of the Investigator and after discussion with the Medical Monitor, it is considered to be the most appropriate site for IT injection. A preferred tumor for IT injection is an accessible lesion that is most rapidly progressing in the judgment of the Investigator. Injected lesions may or may not be target lesions.
- It is allowed to inject all palpable lesions, even if they are all target lesions.
- It is allowed to biopsy injected lesions.

When more than 1 tumor is amenable to IT injection, the Investigator may inject up to 3 tumors per vidutolimod treatment visit. The total dose of vidutolimod may be divided across the tumors at the Investigator’s discretion, and the volume injected into each tumor must be recorded.

- The same tumor(s) should be injected with each individual vidutolimod administration, if possible.

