If an injected tumor is clearly decreasing in size and another accessible noninjected tumor is not, then the Investigator may divide the vidutolimod dose between the 2 tumors or switch from injecting the regressing tumor to injecting the nonresponding (or growing) tumor. Subjects with metastatic disease who have regression of all injectable lesions, or who have an injection site reaction that precludes injection of the tumor, should receive vidutolimod SC near an original tumor (peritumoral) or in the area of the draining lymph nodes (see [Appendix A](#)).

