Appendix Figure 1: Method for Vidutolimod Intratumoral Injection

Recommended Intratumoral Injection Volume Based on Lesion Size

Lesion Size (longest dimension)	Vidutolimod Injection Volume
< 0.5 cm	Up to 0.25 mL
0.5 to 1.5 cm	Up to 0.5mL
1.5 to 2.5 cm	Up to 1 mL
> 2.5 cm	2 mL

Note: 2 mL is the maximum vidutolimod injection volume allowed in up to 3 accessible lesion(s) regardless of the lesion size. If the accessible lesion(s) cannot accommodate the full 2 mL volume, then the remaining volume may be injected peritumorally.

If the full volume cannot be injected within the tumor, the remaining drug volume should be injected into a second accessible tumor, if present; otherwise, the remaining volume should be injected SC near an original tumor (peritumoral). Vidutolimod dose should remain unchanged during the study.

Additional Guidance on Imaging Guided Injection of Vidutolimod

See Intratumoral Injection Manual

Subcutaneous Injection

[figure not shown]
SC administration of Vidutolimod should only occur when all accessible lesions have regressed. vidutolimod SC can be administered within the area of lymphatic drainage corresponding to the site of metastatic disease and follow local standards for SC injection.

In order to maximize the distribution and exposure to vidutolimod, the full volume from a single dose should be distributed to as many SC sites as is practical. It is recommended that equal amounts of drug be injected at each SC site.

Preferred sites of injection include the following (see also [Appendix Figure 2](#)):

- Location of the primary tumor.
- Within the area of lymphatic drainage corresponding to the site of metastatic disease. For example, in a subject with a muscle or bone metastasis in the lower leg, preferred SC injection sites would be in the same leg, with the expectation that at least some of the vidutolimod will drain to lymph nodes that also contain tumor antigens. Likewise, in a subject with metastases in an upper lobe of the lung, a preferred SC injection site would be in the ipsilateral supraclavicular fossa, where the injection may activate pDC in the supraclavicular lymph nodes that also can drain the upper lung.
- Unsuitable sites for injection would include, for example, the palm of the hand or the sole of the foot.

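### Does the missing rule for classing target lesions as injected or noninjected call for a change to SAP 7.2.2?

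*SAP*

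**What the plan says.** The protocol names response in injected and noninjected target lesions as a secondary endpoint (Section 2.2.2). It raises the same question as an exploratory objective: "Evaluate the effect of vidutolimod in combination with cemiplimab on injected and noninjected target lesions" (Section 2.1.3). SAP 7.2.2 gives the analysis one line, "Response in injected and noninjected target lesions by Investigator assessment", and SAP 7.2.3 repeats the exploratory aim. SAP 7.1 defines ORR, DOR, DCR, TTR, PFS and OS but not this endpoint. Protocol 8.6 has no subsection for it, and the summary table in SAP 13.1 has no row.

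On which tumor is injected, Protocol 4.1.1.3.1 sets a default: "The same tumor(s) should be injected with each individual vidutolimod administration, if possible". It then allows two departures. One is a split dose: "If an injected tumor is clearly decreasing in size and another accessible noninjected tumor is not, then the Investigator may divide the vidutolimod dose". The other is a full change of site: "switch from injecting the regressing tumor to injecting the nonresponding (or growing) tumor". Two lesser routes exist. Appendix A says that if one tumor cannot take the full volume, "the remaining drug volume should be injected into a second accessible tumor, if present". Section 3.2.1 says "Treatment beyond the second progression may be allowed in selected cases after communication with the Sponsor", with later injection of a progressing uninjected lesion as its example.

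SAP 1.2 states that there is no formal hypothesis and that the analyses are descriptive and exploratory. Protocol 8.5 and SAP 9.1 list injection location and volume per tumor at each dosing visit.

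**The concern.** Response in noninjected lesions is the readout closest to the rationale for intratumoral dosing. Protocol 1.2.1 cites preclinical work in which it "induced regression not only in the directly injected tumor lesion, but also distant metastases". If an uninjected lesion is injected because it fails to shrink, its group membership depends on its own outcome. Two ways of filling the gap then condition on response:

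- **Never-injected rule.** Lesions that stay flat or grow leave the noninjected group once they are injected.
- **Current-status rule.** The same lesions leave, and after a full switch the regressing lesion that is no longer injected joins the noninjected group.

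Either could make the distant effect look larger than it is. The study is open-label, so an analyst who chooses the rule late could see which choice looks better.

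**Working it through.** The documents give no figure for this endpoint, so there is none to reproduce. The check asks what each plausible rule would do and whether a prescribed rule would do better.

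**Inputs, all assumed.** Each subject has one injected and one noninjected target lesion. The true noninjected response rate is 30%. Of injected lesions, 40% regress, independently of the other lesion. Any nonresponding noninjected lesion (70%) is eligible, and half of eligible pairs are moved. The share of noninjected lesions injected later is

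sw = 0.5 × 0.40 × 0.70 = 0.14.

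Let q be the chance that a moved lesion would have responded without injection, and r its chance of response after injection. Hold sw at 0.14.

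**Status at first intratumoral injection, all measurements kept.** Rate = 0.30 + sw(r − q).
- r = q (later injection has no local effect): 30.0%.
- r = 0.20, q = 0: 0.30 + 0.14 × 0.20 = 32.8%.

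**Never-injected rule.** Rate = (0.30 − sw·q)/(1 − sw), so bias = sw(0.30 − q)/(1 − sw).

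| q | Calculation | Rate |
|---|---|---|
| 0 | 0.300/0.86 | 34.9% |
| 0.10 | 0.286/0.86 | 33.3% |
| 0.20 | 0.272/0.86 | 31.6% |
| 0.30 | 0.258/0.86 | 30.0% |
| 0.40 | 0.244/0.86 | 28.4% |

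The bias is upward only if moved lesions would have responded less often than the average noninjected lesion. Protocol 4.1.1.3.1 moves injections only in subjects whose injected tumor is already shrinking. If response is correlated within subject and uninjected lesions respond late, the moved lesions may be better than average. In a simulation with injected and noninjected rates of 24% and 15%, correlation 0.7, a one-scan lag and every discordant lesion switched, the true rate was 14.9% and the never-injected rate 12.1%.

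**Current-status rule, full switch, every regressing lesion counted as a response.** Rate = 0.30 + sw(1 − q).
- q = 0: 44.0%.
- q = 0.40: 0.30 + 0.14 × 0.60 = 38.4%.

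This bias is never negative. If the dose is divided instead, both lesions are being injected and the result is the never-injected one.

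**Range, at q = 0.** With 40% to 50% of injected lesions regressing, correlation 0 to 0.5, and either growing lesions only (35%) or all nonresponders eligible, sw runs from 0.034 to 0.175.
- Never-injected: +1.1 to +6.4 points.
- Current status: +3.4 to +17.5 points.
- If a tenth rather than half of eligible pairs are moved, as the same-tumor default suggests could happen: +0.2 to +1.1 and +0.7 to +3.5 points.
- No switching: 0.

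**Sampling error for scale.** Cohorts have about 25 subjects. With one noninjected lesion each, 7/25 (28%) has a 95% Clopper-Pearson interval of 12% to 49%.

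**Would a stricter rule do better?** The obvious candidate fixes status at the first intratumoral injection and uses only measurements before a lesion's own first injection. Its rate is 0.30 − sw·q.
- q = 0.10, sw = 0.14: 28.6%.
- q = 0.30: −4.2 points at sw = 0.14 and −5.3 at sw = 0.175, similar in size to the bias it removes.

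All seven weekly doses precede the Week 10 scan, so a lesion first injected in that period has no usable post-baseline scan. Let e be the share of such lesions and w the rate at which they would have responded. Excluding them gives (0.30 − e·w)/(1 − e), and counting them as nonresponders gives 0.30 − e·w. That pair contains 30% only if w is at most 0.30. At e = 0.30 and w = 0.50 it is 21.4% and 15.0%.

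Stopping a subject's whole noninjected sum when one of its lesions is injected discards later data on lesions never injected. With scans every 9 weeks and confirmation required at 4 weeks or more (SAP 7.1), it can also lose the confirming scan.

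**The case for a change.** The best case for a change is that this is a listed secondary endpoint in a SAP that calls itself comprehensive, that classification can follow outcome, and that even the direction of bias is open under one natural rule. In an open-label study the choice is better made before the data are examined, and the cost would be a few lines of SAP text plus mapping injection records to target lesions.

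Much of that stands. There is no rule, and current-status classification after a full switch would mislead. It does not stand that the plan commits to a biased analysis. Counting a lesion that shrank under injection as noninjected strains the word, and an experienced analyst has good reason to avoid it. Between the remaining rules the choice is a real trade-off: fixed initial status can be biased up if late injection works, pre-injection measurements only are biased down, and never-injected can go either way. Nor would a rule settle the scientific question. Every subject receives cemiplimab and there is no control arm, so noninjected response cannot be credited to vidutolimod. The protocol also prefers the most rapidly progressing accessible lesion for injection, so the two groups differ in prognosis from the start. The listings let a reader see where injections were moved, and Protocol Section 8 leaves room to settle details in the final SAP before the first database lock.

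**Conclusion.** No change is needed. This is missing detail on a descriptive endpoint that analysts can fill sensibly, for instance with status at the first intratumoral injection, which is unbiased when later injection has no local effect. The current-status rule would inflate the noninjected rate after a full switch, by 14 points at sw = 0.14 and q = 0. The never-injected rule moves it from +4.9 points (q = 0) to −1.6 (q = 0.40). These sizes rest on an assumed 30% true rate, assumed regression rates and an assumed switching share. They shrink to roughly 0.2 to 3.5 points if only a tenth of eligible pairs are moved, and to zero with no switching. The primary ORR, which does not use injection status, is unaffected. No single prescribed rule is clearly better across plausible values of q, r and the timing of later injections.

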### **7.2.3. Exploratory Efficacy Analyses**

The following exploratory efficacy analyses will be performed for the FAS.

Baseline, and change from baseline, in tumor or blood measurements of biomarkers related to TLR9, immune checkpoints, and potential markers of resistance or response to immunotherapy

Tumor biopsy obtained at baseline and specified time points during the study may be analyzed for protein, RNA, DNA, or other biomarkers related to TLR9, immune checkpoints, and potential markers of resistance or response to immunotherapy.

- Evaluate the effect of vidutolimod in combination with cemiplimab on injected and noninjected target lesions
- To demonstrate treatment induced immune effects consistent with vidutolimod mechanism of action, including TLR9 signaling, increase in pDC activation, corresponding increase in CD8 T cell tumor infiltration, and activation status

## **8. HYPOTHESIS TESTING METHODS AND MULTIPLICITY CONTROL**

There will be no multiplicity adjustment for this study.

## 9. SUMMARY OF EXPOSURE DATA

### 9.1. Investigation Study Drug Exposure and Compliance

Exposure to study drugs will be examined and the following variables will be summarized for each cohort based on the SAF.

The number of CMP-001 and Cemiplimab doses received by each subject will be summarized descriptively by cohort for the Safety Analysis Set. The duration of exposure, dose intensities and relative dose intensity will also be summarized separately as follows with descriptive statistics in a tabular manner and a by-subject data listing.

#### 1. Duration of Exposure

Duration of exposure will be calculated as follows:

Duration of exposure (weeks) = (first dose date of the last cycle received + corresponding cycle duration – first dose date) / 7

- For CMP-001, the corresponding cycle duration = 7 days for Week 1 through Week 6 of Q1W schedule and 21 days for Week 7 and the following Q3W schedule
- As for Cemiplimab, the corresponding cycle duration is 21 days

#### 2. Dosing Intensities

(1) Actual dose intensity (mg/week) will be calculated as the total actual cumulative dose received divided by duration of exposure (weeks) for CMP-001 and Cemiplimab, respectively.

(2) Planned dose intensity (mg/week) will be calculated as the total planned cumulative dose to be received divided by the planned exposure duration (weeks) based on the protocol schedule.

Planned Exposure Duration (weeks) = number of planned treatments \* corresponding cycle duration (weeks)

- For CMP-001, the corresponding cycle duration = 1 week for Week 1 through Week 6 of Q1W schedule and 3 weeks for Week 7 and the following Q3W schedule
- As for Cemiplimab, the corresponding cycle duration is 3 weeks

(3) Relative dose intensity (%) will be calculated based on the actual cumulative dose received relative to the planned cumulative dose throughout the exposure duration as follows:

Relative dose intensity (%) = (actual dose intensity / planned dose intensity) \* 100%

#### 3. Dosage Modifications

The number and percentage of subjects with dose delayed, withheld, interrupted, reduced, permanently withdrawn will be tabulated with the reasons for CMP-001 and Cemiplimab, respectively.

Dosing of CMP-001 and Cemiplimab, including date and time of each dose, route of administration, dose administered, location of each injection, and the volume injected into each tumor at each dosing visit will be presented in a by-subject data listing per the information from the study drug administration eCRFs.

Compliance will be calculated per cohort and by CMP-001 and Cemiplimab as follows:

Treatment Compliance = (Number of doses of study drug administered during treatment period) / (Number of doses planned to be administered during treatment period) x 100%, where temporary dose discontinuation is ignored.

The percentage of subjects who have <60%, 60-80%, 80-100%, and >100% compliance will be summarized for each cohort.

## **9.2. Prior and Concomitant Medications/ Procedures**

Prior medications procedures are defined as those taken within 30 days prior to the first dose date of the study drug and discontinued before the first dose date of the study drug. Prior medications and procedures will be summarized for each cohort based on the FAS. The number and percentage of patients who received any prior cancer related medications, prior cancer related radiotherapy, or prior cancer related surgery will be summarized. Prior cancer related medications will be summarized by setting and ATC levels.

*Concomitant medications.* Concomitant medications are defined as medications which are taken at any time prior to 100 days after the last dose date of the study drug (both CMP-001 and cemiplimab) or until the initiation of an alternative anti-cancer treatment, whichever is earlier. Medications with missing or partially missing start or end dates will be handled according to the conventions described in Data Coventions section. If it cannot be determined whether a medication is a prior medication due to partial medication start or end dates, the medication will be considered concomitant. Treatment medications for study-related AEs that occur more than 100 days after the last dose of study drug will be included as concomitant medications.

Concomitant medications and procedures will be summarized for each cohort based on the SAF. Concomitant medications will be summarized by ATC level 2 and ATC level 4. Patients will be counted once in all ATC categories linked to the medication.

Post-treatment anti-cancer therapy and procedure will be summarized for each cohort based on the SAF, if applicable.

